#### 8.5 Exploratory Analysis

[REDACTED]

[REDACTED]

[REDACTED]

[REDACTED]

[REDACTED]

[REDACTED]

[REDACTED]

run;

## 9 Safety Analysis

In general, baseline measurements of safety variables are defined as their last measurements prior to the randomization for the primary safety population (except for serum creatinine, which is defined similar to the baseline of eGFR assessment for the primary endpoint) and as their last measurements prior to the first dosing of study medication for the secondary safety population. Safety analysis will be conducted based on these safety populations, which are defined in [Section 5.1](#). Standard safety variables to be analyzed include AEs, clinical laboratory tests, and vital signs. In general, summarized statistics of changes from baseline will be provided for safety variables based on all available data. Proposed tables and figures to be generated for the safety analysis can be found in [Appendix 3](#) and [Appendix 4](#).

### 9.1 Adverse Events

All AEs will be coded by system organ class and Medical Dictionary for Regulatory Activities (MedDRA) preferred term. The incidence of the following events will be summarized by treatment group for the primary safety population; summary of these events will also be provided for the secondary safety population:

- a) TEAEs by severity
- b) Potentially drug-related TEAEs
- c) TEAEs with an outcome of death
- d) Serious TEAEs
- e) Discontinuations due to TEAEs

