3.7.1.2 Double-blind, Randomized Treatment Period (Day 0 to Month 12)

Day 0 is the beginning of the double-blind, randomized treatment period. Only subjects who reach Day -1 and are able to tolerate a given dose of tolvaptan “for the rest of their

lives” at a level of 60/30 mg or 90/30 mg will be eligible to enter this period. In this period, neither the subject nor the investigator or his/her staff will know with certainty which treatment is assigned. Immediately prior to randomization, and at each subsequent visit or site contact, the subject will be reminded of the importance of their commitment to continue participation in the trial; however, the subject will not be told that this day is the point at which randomization to long-term therapy occurs.

Post-randomization, the maximally-tolerated dose of tolvaptan established during the run-in period, or the equivalent as matching placebo tablets, will be dispensed according to the subject’s randomization outcome. Subjects must return any unused IMP from the pre-randomization period before continuing in the double-blind, randomized treatment period.

From this point forward, every effort to maintain adherence and continuation of the subjects until the end of the trial should be undertaken. If continued tolerability becomes an issue, subjects may titrate downward to 45/15 mg or 30/15 mg (with medical monitor approval) or temporarily interrupt treatment as needed. Return to higher doses is also allowed.

Assessments during the double-blind, randomized treatment period will include (See [Table 3.7-1](#)):

- 1) Remind the subject of the importance of their commitment to continue participation in the trial at all visits
- 2) Record concomitant medications at all visits
- 3) Assess AEs at all visits
- 4) Assess vital signs (including sitting heart rate and blood pressure) at Month 3, 6, 9, 12/ EoTx visits; include assessment of post-void body weight at the Month 12/EoTx visit only
- 5) Perform a full physical examination at Month 12/EoTx visit only (directed physical exam may be performed at Month 3, 6, 9 visits, if deemed necessary by the investigator)
- 6) Urine pregnancy test for WOCBP at Month 3, 6, 9, 12/EoTx visits (or if indicated)
- 7) Collect urinalysis sample at the Month 12/EoTx visit

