- 8) Collect blood for serum creatinine for eGFR calculation and for assessment of sodium and liver function panel (see [Section 3.7.3.2](#)) monthly and at the Month 12/EoTx visit. Serum sodium and liver function panel should be determined from the same blood sample.
- 9) Collect blood for serum chemistry assessment at the Month 12/EoTx visit. The sodium, serum chemistry and liver function panel should be determined from a single tube of blood.

- 10) Collect plasma samples for PK analysis and PD urine samples at Month 3, 6, 9, 12/EoTx visits
- 11) Collect plasma and urine samples for potential biomarker analysis at Month 3, 6, 9, 12/EoTx visits (see [Section 3.7.3.5](#))
- 12) Complete PKD outcomes survey (monthly and at the Month 12/EoTx visit)
- 13) Ask subject “Can you tolerate this dose of trial medication for the rest of your life?” at each visit
- 14) Update subject status in IVRS (monthly and at the Month 12/EoTx visit)
- 15) Dispense IMP at monthly visits up to and including Month 11. In certain circumstances, with medical monitor approval, a 3-month drug supply may be provided; however, initiation of the next month’s supply must be directed by the site.
- 16) IMP reconciliation (monthly and at the Month 12/EoTx visit)
- 17) Subjects not continuing in this trial must have a 21-day follow-up period (see [Section 3.8.3.3](#)).

Visits during the treatment period will be scheduled monthly (± 2 days), with a final visit at Month 12/EoTx.

Regardless of discontinuation of IMP, the subjects are expected to complete all monthly visits and assessments including the Month 12 visit (see [Section 3.8.3.3](#)).

All subjects have the right to withdraw their consent from further participation in the trial at any time without prejudice. In all cases of impending IMP discontinuation or consent withdrawal, the investigator should follow the procedures outlined in [Section 3.8.3.5.1](#) to determine if the subject can continue participation in the trial if modifications to his/her treatment and/or schedule of assessments can be accommodated.

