7.6 Safety Analysis

In general, baseline measurements of safety variables are defined as the last measurements prior to randomization for the primary Randomized Safety Population (except for serum creatinine, which is defined similarly to the baseline of eGFR assessment for the primary endpoint, see [Section 7.4.1.1](#)) and as their last measurements prior to the first dose of IMP for the secondary safety population (Treated Safety Population).

Standard safety variables to be analyzed include AEs, self-reported tolerability, clinical laboratory data, physical examinations, and vital signs. Safety variables will be summarized by descriptive statistics, (eg, proportion, mean, median, SD, minimum, and maximum values). In general, summary statistics, including changes from baseline, will be provided for safety variables based on all available data.

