7.6.1 Adverse Events

All AEs will be coded by system organ class and Medical Dictionary for Regulatory Activities (MedDRA) preferred term. The incidence of the following events will be summarized by treatment group for the primary safety population; summary of these events will also be provided for the secondary safety population:

- a) Treatment-emergent AEs (TEAEs) by severity
- b) TEAEs potentially causally related to the IMP
- c) TEAEs with an outcome of death
- d) Serious TEAEs
- e) Discontinuations due to TEAEs

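### The by-arm TEAE incidence planned in SAP 9.1 cannot show aquaretic AEs that persist from run-in on tolvaptan but resolve on placebo

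*SAP*

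**What the plan says.** SAP 9.1 lists five adverse event (AE) summaries, all of TEAEs: by severity, drug-related, fatal, serious, and leading to discontinuation. They are to be "summarized by treatment group for the primary safety population; summary of these events will also be provided for the secondary safety population". Protocol 7.6.1 gives a matching list, starting with "Treatment-emergent AEs (TEAEs) by severity". Neither document says when an event becomes treatment-emergent, or how to count one already ongoing at randomization.

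In SAP Appendix 3 the term-level double-blind tables also count TEAEs. CT-8.1.2.1 is by system organ class and preferred term; CT-8.6.1 screens terms by incidence thresholds and Fisher's exact test. The CT-8.2 tables report AEs from the single-blind tolvaptan period, which has no control arm.

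SAP 9 takes the safety baseline from the "last measurements prior to the randomization for the primary safety population", when both arms are on tolvaptan.

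The documents differ on tolerability. Protocol 7.6 says: "Standard safety variables to be analyzed include AEs, self-reported tolerability, clinical laboratory data". Protocol 3.7.1.2 has subjects asked at each randomized visit: "Can you tolerate this dose of trial medication for the rest of your life". SAP 9 says only: "Standard safety variables to be analyzed include AEs, clinical laboratory tests, and vital signs". Appendix 3 lists no tolerability table.

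**The concern.** A secondary objective (SAP 2.2) is to compare overall safety with placebo, and only the randomized period has a concurrent control. Protocol 1.3 names polyuria, pollakiuria, nocturia, thirst and dry mouth as the five most frequently reported AEs. Protocol 1.4 says aquaretic reactions come early and are the ones most likely to limit continued therapy. In this withdrawal design their usual onset window falls before randomization. After that, the informative contrast is whether symptoms continue on tolvaptan and stop on placebo. Incidence counts starts, so it is blind to that contrast.

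The plan does deal with the same carry-over for creatinine: SAP 9 exempts it from the pre-randomization baseline, and Appendix 1 grades later values against the run-in period matching the assigned arm. AEs get no comparable step. Protocol 1.3 expects weaker aquaretic effects as renal function declines, so a small TEAE difference produced by the design could be taken as confirming that.

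**Working it through.** The plan states no AE rate, so there is no figure to reproduce. The check is a count by arm.

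**Inputs from the documents**
- Titration, Day -35 to -22 (Protocol 3.2.1.3): 14 days. Run-in, Day -21 to -1 (Protocol 3.2.1.4): 21 days. 14 + 21 = 35 days of tolvaptan in every randomized subject.
- 1:1 allocation to continue or to switch to matching placebo (Protocol 3.2.2). About 1300 randomized, so 1300 / 2 = 650 per arm.

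**Assumed quantities (no rates are given)**
- p0: share with the AE at randomization, equal between arms in expectation.
- u: share of those in whom it persists unchanged at Month 1; w: share in whom it worsens.
- n: new-onset share among the rest.
- For simplicity, new and worsened events are taken as still present at Month 1.

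**Difference, tolvaptan (T) minus placebo (P)**
- A, TEAE means onset or worsening after randomization: p0(wT - wP) + (1 - p0)(nT - nP).
- B, TEAE dated from first tolvaptan dose: (1 - p0)(nT - nP). Carried-over events add p0 to each arm and cancel.
- C, AE present at Month 1: p0[(uT + wT) - (uP + wP)] + (1 - p0)(nT - nP).

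u appears in neither A nor B, so the result does not depend on the missing onset rule. The amount omitted under A is C - A = p0(uT - uP).

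**Extreme case.** p0 = 40%, uT = 1, uP = 0, no new or worsened events. A counts 0% v 0% and B counts 40% v 40%, so both differences are 0. C is 40% v 0%.

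**Range of p0(uT - uP), in points**

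| uT - uP | p0 = 10% | p0 = 50% |
|---|---|---|
| 0 | 0 | 0 |
| 0.1 | 1 | 5 |
| 0.3 | 3 | 15 |
| 0.8 | 8 | 40 |

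**Worked example (all rates assumed).** p0 = 0.3, nT = 0.15, nP = 0.10, w = 0.05 in both arms.
- A: 0.3 x 0.05 + 0.7 x 0.15 = 12.0% v 0.3 x 0.05 + 0.7 x 0.10 = 8.5%; difference 3.5 points.
- B: 30 + 10.5 = 40.5% v 30 + 7 = 37.0%; difference 3.5 points.
- C depends on persistence:

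| uT, uP | T v P at Month 1 | Difference (95% CI) |
|---|---|---|
| 0.4, 0.4 | 24.0% v 20.5% | 3.5 (-1.0 to 8.0) |
| 0.5, 0.4 | 27.0% v 20.5% | 6.5 (1.9 to 11.1) |
| 0.5, 0.2 | 27.0% v 14.5% | 12.5 (8.1 to 16.9) |
| 0.8, 0 | 36.0% v 8.5% | 27.5 (23.2 to 31.8) |

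The TEAE difference stays at 3.5 points in every row.

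**Precision of a prevalence table.** Half-width 1.96 x sqrt(2p(1 - p)/650): 3.3 points at p = 10%, at most 5.4 points (p = 50%).

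**The case against.** The strongest reply is that onset-independent comparisons are already planned. CT-2.2 tabulates reasons for stopping treatment, and SAP 8.3 item 12 maps CRF reason 1.1 (not tolerable) to aquaretic AE. Figure 9.2 shows time to stopping IMP. CT-7.2.1 shows exposure by daily dose, which would reveal down-titration. Protocol 6.2 summarizes urine osmolality by arm against a baseline taken before any tolvaptan. This stands: these outputs show by arm whether aquaresis continues and whether it drives subjects to stop or step down. They do not show how many subjects who stay on treatment still have thirst or nocturia.

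Second, the run-in exists to remove subjects who cannot tolerate aquaresis (Protocol 2.1), the safety endpoints are descriptive (3.5.2.2), and Protocol 1.4 calls the risks well characterized from earlier work. That explains the design and limits the weight of the point. It does not make the incidence difference a measure of aquaretic risk.

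Third, every rate above is assumed. Placebo persistence could be high, because all subjects are told to drink at bedtime and after nocturia (Protocol 3.2) and urine concentration defects belong to the disease (Protocol 5). Aquaresis falls about 20% by the fifth day of dosing (Protocol 2.2), and urine volume is lower at lower eGFR (1.3). This stands too: the gap may be zero.

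Fourth, some text is redacted (exploratory safety endpoints, SAP 8.5) and Appendix 3 lists proposed tables. The statement that no persistence table exists rests on the readable text.

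**Conclusion.** The point holds as a limitation of the planned comparison. Events carried over unchanged contribute nothing to the TEAE difference under either usual onset rule, so defining TEAE would not cure it. The omitted amount is p0(uT - uP). It cannot be sized from the documents and has a floor of zero; the 0 to 40 points rest on assumed p0 of 10% to 50% and persistence gaps of 0 to 0.8.

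A reader might infer three stronger things that the documents do not support:
- That aquaretic AEs vanish from the report. New and worsened events count in the double-blind tables, and the CT-8.2 tables give run-in incidence, though without a control.
- That the understatement is known to be large. No run-in rate or persistence figure is given.
- That the SAP fixes TEAE onset at randomization. The baseline rule in SAP 9 concerns measurements. The double-blind table titles make that reading likely, but it is not written.

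The missing tolerability summary is a plain mismatch between protocol and SAP and is worth correcting in its own right. Efficacy and type I error are unaffected. This is an improvement to consider.

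**What to change.** 1. Restore self-reported tolerability to SAP 9 as a table by arm and visit, as Protocol 7.6 commits.
2. Add one by-arm table for thirst, polyuria, nocturia, pollakiuria, polydipsia and dry mouth (the last is absent from the aquaretic list in SAP 8.2.4). Give point prevalence, meaning the AE is ongoing whatever its onset date, at fixed visits such as Months 1, 3, 6 and 12, with risk difference and 95% CI. Show subjects who stopped IMP for that AE in a separate row and also count them as having the event; otherwise someone who stops before Month 1 and recovers would look event-free. Leave new onset in the existing TEAE tables, so that prevalence and cumulative incidence are not mixed.
3. In the CT-8.1.6 and CT-8.1.7 tables, count AEs leading to post-randomization discontinuation or down-titration whatever their onset date.
4. State in SAP 9.1 that the TEAE difference alone does not estimate aquaretic risk versus placebo.

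No new data are needed. Protocol 3.7.1.2 requires sites to "Assess AEs at all visits", duration and outcome are recorded (Protocol 9.2), events open at last contact are marked ongoing (5.6.1), and subjects who stop IMP are expected to keep attending through Month 12 (3.8.3.3).

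The cost is two tables, one counting rule and one sentence. There are three drawbacks. "Visits during the treatment period will be scheduled monthly", so stop dates may be recorded late. Reported resolution may be affected by subjects guessing their assignment, a limitation that Protocol 3.6 acknowledges. The tolerability figure for tolvaptan may look less favourable.

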### 9.2 Clinical Laboratory Data

Summary statistics for changes from baseline in the central clinical laboratory measurements will be provided for the primary and secondary safety populations. Potentially clinically significant results in laboratory tests identified using prospectively defined criteria will also be summarized for the primary and secondary safety populations as well. Criteria of potentially clinically significant lab test abnormalities are provided in [Appendix 1](#).

In addition, laboratory measurements that signal the potential for Hy's Law will be reported. An incidence table and a listing will be provided for subjects who meet one or combinations of following criteria, without initial findings of cholestasis (serum alkaline phosphatase (ALP) activity >2xULN):

Protocol 156-13-210

Alanine aminotransferase (ALT) or aspartate aminotransferase (AST)  $\geq$  3x upper limit of normal (ULN)

Bilirubin  $\geq$  2x ULN

### **9.3 Physical Examination, and Vital Signs Data**

By-patient listings will be provided for physical examination. Summary statistics for changes from baseline in vital signs and potentially clinically significant results in vital signs will be summarized for the primary safety population as well as the secondary safety population.

Incidence of potentially clinically significant vital sign results will also be summarized by treatment groups. Criteria of potentially clinically significant vital sign abnormalities are provided in [Appendix 2](#).

## **10 Interim Analysis**

An optional interim analysis was planned but will not be conducted, because, given the rapid final enrollment, the sponsor, upon receiving recommendation from the trial's Steering Committee, deemed the analysis might only bring a few month's difference in trial conclusion. Thus, without the interim analysis, the alpha level of the final analysis will be 0.05.

**Laboratory Test Abnormalities due to Test Value Increase**

Test	Abnormality	Test Result Grade				
		0	1	2	3	4
APTT (sec)	Increase	ULN	> ULN - 1.5xULN	> 1.5xULN - 2xULN	> 2xULN	
ALT (SGPT) (IU/L)	Increase	ULN	> ULN - 3xULN	> 3xULN - 5xULN	> 5xULN - 20xULN	> 20xULN
AST (SGOT) (IU/L)	Increase	ULN	> ULN - 3xULN	> 3xULN - 5xULN	> 5xULN - 20xULN	> 20xULN
Bilirubin, Total (mg/dL)	Increase	ULN	> ULN - 2xULN	> 2xULN - 3xULN	> 3xULN - 10xULN	> 10xULN
Creatinine (mg/dL)	Increase Pre-randomization	AB*	> AB - 1.5xAB	> 1.5 x AB - 3 x AB	> 3 x AB - 6 x AB	> 6 x AB
Creatinine (mg/dL)	Increase Post-randomization	< 1.33 x PR*	1.33 x PR - < 2x PR	2 x PR - < 3 x PR	3 x PR - 6 x PR	> 6xPR
Eosinophils, Absolute (Thous/ $\mu$ L)	Increase	$\leq 0.65$	> 0.65 - 1.5	> 1.5 - 5	> 5	-
Glucose (mg/dL)	Increase	$\leq 115$	> 115 - 160	> 160 - 250	> 250 - 500	> 500
Hemoglobin (g/dL)	Increase	ULN	> ULN - 20	> 20 - 21	> 21 - 22.5	> 22.5
Potassium (mEq/L)	Increase	ULN	> ULN - 5.5	> 5.5 - 6	> 6 - 7	> 7
INR	Increase	ULN	> ULN - 1.5xULN	> 1.5xULN - 2xULN	> 2xULN	-
Sodium (mg/dL)	Increase	< 145	146 - 150	151 - 155	156 - 160	> 160
Triglycerides (mg/dL)	Increase	ULN	> ULN - 2.5xULN	> 2.5xULN - 5xULN	> 5xULN - 6xULN	> 6xULN
Urea Nitrogen (mg/dL)	Increase	$\leq 22$	> 22 - 26	> 26 - 31	> 31	-
White Blood Count (Thous/ $\mu$ L)	Increase	$\leq 10.799$	> 10.799 - 15	> 15 - 20	> 20 - 25	> 25

\* Baseline creatinine is expected to be elevated in this population. Average baseline (AB) is equal to the mean baseline value collected during screening period.

During treatment with tolvaptan, serum creatinine is expected to increase by approximately 5 to 10%. Post-randomization baseline (PR) is equal to the highest value obtained during the run-in period matching the subject's assigned treatment, ie, either placebo or tolvaptan run-in periods.

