Renal impairment reduces tolvaptan clearance and consequently plasma concentrations increase. Following a single 60 mg dose, tolvaptan AUC in subjects with ██████████ higher compared to subjects with ██████████. Tolvaptan is highly bound to plasma proteins (> 98%) and binding was unaffected by renal impairment.

Pharmacodynamic (PD) responses to tolvaptan were observed for subjects with ADPKD at CKD stages 1 to 4. At the recommended split-dose regimens of 45/15 mg to 90/30 mg daily, tolvaptan blocked AVP action at the V_2 receptor (ie, increased urine excretion rates and suppressed U_{osm}) for almost the entire 24-hour day in subjects with ADPKD (CKD Stage 1 to 2). The large increase in urine output that resulted from this inhibition was associated with the 5 most frequently reported adverse events (AEs; polyuria, pollakiuria, nocturia, thirst, and dry mouth) in clinical pharmacology or clinical efficacy trials. In 2 clinical pharmacology trials in subjects with ADPKD and estimated glomerular filtration rates (eGFR) > 60 mL/min/1.73m² administered a 90/30 mg dose regimen for at least 7 days, mean (standard deviation [SD]) 24-hour urine volumes were 7.464 (2.103) L and 6.532 (2.036) L. As renal function declined, the volume of urine produced for a given dose of tolvaptan decreased; following a 90/30 mg split-dose regimen, mean (SD) 24-hour urine volumes for subjects with ADPKD and eGFR 30 to 60 and < 30 mL/min/1.73m² were 6.233 (1.307) L and 5.024 (1.767) L, respectively. Therefore, despite an increase in tolvaptan concentration, the clinical effects of tolvaptan on the most common adverse events are diminished. Other adverse reactions, such as idiopathic liver injury, do not appear to be concentration-dependent.

Subjects with ADPKD are able to maintain a neutral fluid balance so increases in serum sodium and plasma osmolality were small, following tolvaptan treatment. Serum concentrations of creatinine, cystatin C, and uric acid were higher following tolvaptan treatment as tolvaptan reduced the eGFR approximately 6 to 8%, CrCL approximately 8 to 10%, and uric acid clearance approximately 20 to 25%; the changes appeared to

independent of baseline renal function for CKD stages 1 to 4. Urinary excretion of aquaporin 2 and cAMP were lower following tolvaptan treatment, supporting the hypothesis that tolvaptan inhibition of the V₂ receptor is successful in reducing cellular cAMP concentrations.

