1.4 Known and Potential Risks and Benefits

ADPKD is a devastating, progressive disease that places a tremendous burden on patients and their families. The risk a patient is willing to accept is a personal decision based on his/her individual and familial experience with the disease. Tolvaptan is potentially the first therapy that offers patients a treatment option to slow their disease progression; however, as of January 2014, it has not yet been approved for this indication. The treatment risks are well characterized, manageable, and must be weighed against the consequences of no treatment.

The most common observed risks of tolvaptan therapy include those arising from aquaresis (eg, polyuria, pollakiuria, nocturia, thirst, dry mouth), dehydration, electrolyte abnormalities, and gout. While aquaretic events did not contribute to significant patient morbidity over 3 years of study in the pivotal placebo-controlled trial (Trial ██████████), they do represent adverse drug reactions (ADRs) which occur early (within days to weeks) and are most likely to limit a subject's ability to continue therapy over a duration of treatment that is likely to provide benefit. Aquaretic ADRs are also likely to limit the efficacy of an unproven, yet often recommended, therapeutic strategy of increasing water ingestion.

While the proposal of increased water ingestion as a mechanism of ameliorating CKD¹⁰ has not reached medical equipoise, in this trial we believe a general recommendation to do so is reasonable and would recommend ingestion of water adequate to avoid thirst. Typically, this would represent a minimum of 2 to 3 liters of water per day in subjects with relatively intact renal function, and lesser amounts in those with more impaired

function. Serum sodium should be monitored during the trial to ensure a tendency toward hyponatremia (symptomatic or asymptomatic) is not produced.

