Hematology and coagulation panel: 
 • hemoglobin, • mean corpuscular hemoglobin (MCHC) • mean corpuscular volume (MCV) • red blood cell (RBC) count • white blood cell (WBC) count with differential • platelet count • prothrombin time (PT) as international normalized ratio (INR) • activated partial thromboplastin time 	Serum chemistry panel: 
 • albumin • blood urea nitrogen (BUN) • serum calcium • serum chloride • carbon dioxide (CO₂) • gamma-glutamyl transpeptidase (GGT) • glucose • lactate dehydrogenase (LDH) • phosphorus • potassium • total cholesterol • total protein • uric acid
Liver function panel: 
 • alkaline phosphatase (ALP) • alanine transaminase (ALT) • aspartate aminotransferase (AST) • direct bilirubin • total bilirubin (BT) 	Urinalysis panel: 
 • appearance • color • blood • glucose • microscopic analysis (including WBC/RBC counts per high-powered field) • pH • protein • osmolality • specific gravity • urine creatinine
Creatinine	Sodium

Liver panels will be analyzed more frequently during the double-blind, randomized treatment period if ALT > twice the upper limit of normal ($2 \times$ ULN), using both central and local laboratories, as needed, and per standard of care according to the subject's individual medical needs. If liver function panel, sodium and/or serum chemistry assessments are scheduled at the same visit, all values should be determined from the same blood sample.

Urine pregnancy testing will be performed with commercially available, high-sensitivity kits supplied to the subject by the site (acquired by the sponsor or through the central laboratory for uniformity). Female subjects who are capable of bearing children will have their urine tested in clinic prior to trial entry (screening period) and at visits for

Months 3, 6, and 9 during the double-blind randomized treatment period. Once enrolled into the trial, the subject should contact the clinic immediately on suspicion of pregnancy, and unscheduled urine or blood pregnancy testing will be performed. Positive urine pregnancy tests should be confirmed with a serum pregnancy test.

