The following serum chemistry laboratory tests may be performed by the central laboratory at the request and approval of the medical monitor: calcium, phosphorus, parathyroid hormone, vitamin D, and bicarbonate levels. If performed, the results from these tests will be included in the clinical database.

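### SAP Appendix 1 has no uric acid criterion, so the double-blind abnormality tables cannot count a laboratory effect that the protocol itself predicts (minor)

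*SAP*

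**What the plan says.** **What the protocol expects.** Protocol 1.3 reports that "Serum concentrations of creatinine, cystatin C, and uric acid were higher following tolvaptan treatment", and gives the size of the renal handling effect as a reduction in "uric acid clearance approximately 20 to 25" per cent. Protocol 1.4 includes "dehydration, electrolyte abnormalities, and gout" among the most commonly observed risks.

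**What is measured.** The serum chemistry panel in Protocol Table 3.7.3.2-1 ends with "total cholesterol • total protein • uric acid". Total cholesterol is its only lipid. Section 3.7.3.2 also allows tests at the medical monitor's request, namely "calcium, phosphorus, parathyroid hormone, vitamin D, and bicarbonate levels". Triglycerides are in neither list.

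**When it is measured.** Protocol 3.7.1.2 says: "Collect blood for serum chemistry assessment at the Month 12/EoTx visit". Table 3.7-1 and Section 3.7.3.2 agree that this is the only on-treatment panel. Footnote f to Table 3.7-1 also places the full panel at Months 3, 6 and 9.

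**How it is reported.** SAP 9.2 covers "Potentially clinically significant results in laboratory tests identified using prospectively" defined criteria and sends the reader to Appendix 1 for them. Neither the increase table nor the decrease table there has a uric acid row. The increase table has a row for "Triglycerides (mg/dL". Neither table shows a redaction.

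**The concern.** Appendix 1 decides which laboratory values the abnormality listings and incidence tables can show. An analyte without a row cannot appear in them, whatever its values. Uric acid is one of the few analytes for which the protocol states both a direction and a size of drug effect, and it names a related clinical risk.

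A mean change from baseline does not show how many subjects reach a high level, and it is the subjects at the high end who matter for gout. Without a row, the safety comparison has no by-arm count of high uric acid against a limit set in advance. A limit chosen after unblinding would not be prospectively defined, which both SAP 9.2 and Protocol 7.6.2 promise.

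**Working it through.** No figure in the plan needs reproducing here. The check compares lists, with one small calculation for scale.

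**1. Appendix 1 against the protocol's laboratory lists.** An analyte counts as measured if it appears in Table 3.7.3.2-1 or among the on-request tests, at any visit. The white cell differential is taken to cover eosinophils, lymphocytes and neutrophils.

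| Item | Count |
|---|---|
| Increase rows in Appendix 1 | 15 (creatinine has two) |
| Decrease rows in Appendix 1 | 8 |
| Distinct analytes graded | 17 |
| Of these, in a protocol laboratory list | 16 |
| Graded but in no list | 1 (triglycerides) |
| Serum chemistry panel analytes | 13 |
| Of these, graded | 3 (urea nitrogen, glucose, potassium) |
| Not graded | 13 − 3 = 10, uric acid among them |

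**2. Where uric acid can appear in the double-blind outputs listed in SAP Appendix 3.**

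- CT-10.2.2.1, CT-10.2.2.2 (listings) and CT-10.2.3.1 (incidence): not possible, because no criterion exists.
- CT-10.2.4.1 (mean change, serum chemistry): yes, as a mean.
- CT-8.1.2.1 (adverse events by preferred term) and CT-8.6.1 (imbalance screen): yes, as gout or as a laboratory change that the investigator records as an adverse event.
- CT-8.5.1.1 to CT-8.5.1.8 (special-interest events): no. They cover liver, skin tumours and glaucoma.

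**3. What a new row could grade.** The scheduled pre-randomization panel is at screening V1, before any tolvaptan, so the uric acid baseline is drug-free in both arms. On treatment, the schedule table and visit lists give one value per subject (Month 12/EoTx). Footnote f gives up to four (Months 3, 6, 9 and 12/EoTx). Urea nitrogen, glucose and potassium come from the same panel and are graded, so the sampling schedule does not explain the omission.

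**4. Scale, as illustration only.** Assume steady state, unchanged uric acid production and purely renal elimination. The documents state none of these. Serum level is then proportional to 1/clearance:

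- clearance down 20%: 1/0.80 − 1 = 0.25, a 25% rise
- clearance down 25%: 1/0.75 − 1 = 0.33, a 33% rise

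If part of the elimination is non-renal and unaffected, the rise is smaller. Without a baseline distribution, this does not say how many subjects would cross any limit.

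**The case against.** **The adverse event route covers much of this.** Under Protocol 5.1 the investigator reviews every laboratory result, and a change judged clinically significant for that subject is an adverse event. Gout is an adverse event in its own right. CT-8.6.1 then screens all treatment-emergent events for imbalance: tolvaptan at least 1% and at least 0.5% above placebo, or below 1% and more than twice placebo, or a significant Fisher test. This stands, and it is the main reason the point is minor. A reader might infer that gout or raised uric acid would be invisible in the safety report; the documents do not support that. What this route cannot give is a count by one fixed rule, since it depends on each investigator's judgement.

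**Choosing analytes is the sponsor's decision.** Ten of the 13 panel analytes are ungraded, and the laboratory endpoints named in Protocol 3.5.2.2 do not mention uric acid. That also stands: a missing row is not an error in itself. Uric acid differs because the protocol predicts the effect with a size and names a related risk. Appendix 1 was also adapted to this drug: its creatinine grades are relative to baseline, and a footnote cites the 5 to 10% creatinine rise expected on tolvaptan.

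**The single-blind tables.** A reader might extend the point to CT-10.3.3.1. The schedule draws no chemistry panel during titration or run-in. Apart from EoTx samples in run-in failures (Protocol 3.8.3.1), there would be almost nothing to grade, so the point does not reach that table.

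**The triglycerides row.** It flags nobody and biases nothing. It is clutter, and no document gives a reason to put total cholesterol in its place.

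**Grading by ULN alone.** The SAP avoids this for creatinine because baseline is expected to be elevated. Uric acid may also be raised before treatment at eGFR 25 to 65 mL/min/1.73 m², so the objection stands and shapes the fix.

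**Conclusion.** The point holds and is minor. Appendix 1 lacks a uric acid criterion, and three double-blind outputs (CT-10.2.2.1, CT-10.2.2.2 and CT-10.2.3.1) therefore cannot flag a raised value in either arm. What is lost is a prospectively defined, by-arm count and listing of high uric acid. The mean change and the reported events remain.

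This rests on the protocol's laboratory lists being complete and on Appendix 1 being the full set of criteria. A reader might take the 25 to 33% rise as the expected effect in this trial. The documents do not support that, because the figure depends on the three assumptions stated with it. No efficacy result or error rate is affected.

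**What to change.** 1. Before unblinding, add a uric acid increase row to SAP Appendix 1 for the double-blind tables. Define the grades so that they allow for elevated pre-treatment values, for example relative to the subject's screening value as well as to the central laboratory's ULN. This follows the baseline-relative approach already used for creatinine. The documents supply no cut-offs, so the sponsor must set and justify them. The creatinine reference taken from the run-in periods cannot be copied, because no uric acid sample is scheduled there.
2. Delete the triglycerides row. This is a tidy-up with no effect on results.
3. Reconcile footnote f to Protocol Table 3.7-1 with the schedule table, Section 3.7.1.2 and Section 3.7.3.2 on when the chemistry panel is drawn. The answer sets how many values per subject the new row can grade.

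Items 1 and 2 cost one row added, one row removed and a program change. They need no new samples.
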